SaliPen - Human Factors Study for OTC labeling

Test Product:	SaliPen
Sponsor's Name:	Saliwell Ltd.
Sponsor's Address:	[name]
Sponsor's Telephone Number:	Tele# [name]
Sponsor's Fax Number:	Fax# ([contact]
Study Number and version:	1
Version Date:	August 31, 2021

Table Of Content

1. Investigators' Statement	3
2. Study Synopsis	4
3. Study Objective and Rationale	5
3.1. The study objective	5
3.2. The study rationale	6
4. Brief Study Description	6
5. Detailed Study Description	6
5.1. Phase I	6
5.2. Phase II	7
6. Study Design	7
7. Arms and Interventions	7
8. Features to be studied	8
9. Outcome Measures	8
10. Eligibility Criteria	8
10.1. Inclusion criteria:	8
10.2. Exclusion criteria:	8
11. Reportable Events	9
12. Contacts and Locations	9
13. Task Analysis	9
14. Ethical and Legal Aspects	10
14.1. Compliance with Regulations Applicable to Clinical Trials	10
14.2. Informed Consent	10
14.3. Institutional Review Board (IRB)	11
14.4. Protocol Amendments	11
14.5. Subject Confidentiality	11
15. Guide for participants	12
16. Evaluation Sheets	14

1. Investigators' Statement

I have read the protocol:

A Clinical Study Evaluating the SaliPen Usability Engineering Study for OTC labeling

that contains all the information necessary for the conduct of the study. I agree to conduct the study as outlined therein and in accordance with the Declaration of Helsinki 1964 and all its updates.

The undersigned confirms that I agree to conduct the study under the conditions described in this protocol:

Principal Investigator (Print Name)

Date (dd / mm / yy)

Principal Investigator's Signature

2. Study Synopsis

Protocol Number	21-D-246
Study Title:	SaliPen Human Factors Study for OTC labeling
Number of Centers:	One center
Countries:	USA
Study Duration:	The expected duration of the study for each subject on each Phase is about one day.
Total Study Duration:	TBD
Expected Subject Enrollment:	The total expected enrollment is 16 subjects for Phase I and 16 for Phase II.
Study Population:	Subjects attending an oral health clinic.
Study Objectives:	
The primary objective of this research is to assess the human factors in relabeling the SaliPen from a prescription-based device to an OTC.
 
Primary performance endpoints:
 
• The user can select the device properly.• The user can use the device as instructed in the IFU.
Study Design:	
This will be a single-center, prospective, open-label study.
 
Screening: Eligible subjects will be included in the study.

Test Participant Recruitment Plan:	
Patients visiting the participating clinic will be asked to participate in the study sequentially (by order of recall or arrival at the clinic).
 
For Phase I, enrollment will be stopped once the goal of eight (8) subjects with xerostomia and eight (8) subjects without xerostomia has been reached.
 
For Phase II, 16 subjects with xerostomia that are evaluated or treated at the clinic will be enrolled sequentially (by order of recall or arrival at the clinic). Patients that have participated in Phase I and have xerostomia will be invited to participate in Phase II, as well.
 
Participants will receive \$25 cash for participating in either phase of this study. Participants in both phases will receive \$50 cash.

	Participants in Phase II will be given the option to keep the SaliPen device they will use in the study.
Inclusion Criteria:	Phase I: Any adult person that is 18 years old or older Phase II: Subjects with xerostomia that are 18 years old or older
Exclusion Criteria:	Phase I: 
• Children and adolescents (persons under 18 years of age)• Persons with experience in the use of SaliPen Phase II: 
• Persons with experience in the use of SaliPen• Children and adolescents (persons under 18 years of age)• Epileptic disorder• Persons that are allergic to the surface materials of the device
◦ Electrodes: coated with gold◦ Body: made of methyl vinyl silicone rubber• Use of a pacemaker• Pregnancy• Psychiatric or psychological disorders• Involuntary muscle movement disorder (such as Parkinson's)• Neurologic disorder in head and neck area
Medical Device Description:	Electrical salivary stimulator system.
Study Endpoints:	Performance Endpoints: 
• Correct selection of the product.• Product use in accordance with the IFU.
Statistical Analysis	A simple descriptive statistical analysis will be utilized to calculate the percentage of correct answers and the percentage of subjects that passed the evaluation in each phase of the study.

3. Study Objective and Rationale

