5.2. Phase II

The study product will be dispensed only to those subjects who will indicate that they volunteerize to participate in this phase of the study.

At Phase II subjects with xerostomia and that are willing to try the study product, will be requested to use it with no training, except for their understanding of the User Manual (internal labeling). Those subjects will use the study product in a supervised clinical setting. Subjects who report any discomfort will be offered the option to pause and remove the device upon such a request.

Correct use verification will be performed by the study investigators. Subjects will answer questions regarding product use, clarity of the IFU, ease of use, etc. Subjects will also receive an exam of their oral cavity.

6. Study Design

Study Type:	Interventional (Clinical Trial)
Enrollment:	Phase I: 16 participants, 8 with xerostomia and 8 without xerostomia
	Phase II: 16 participants with xerostomia (may include participants in Phase I with xerostomia)
Allocation:	N/A
Intervention Model:	Single Group Assignment
Masking:	None (Open Label)
Primary Purpose:	Human Factor Validation - Usability Engineering assessment for OTC labeling
Official Title:	SaliPen Usability Engineering Study for OTC labeling
Study Start Date:	TBD

According to the FDA Guidance document “Applying Human Factors and Usability Engineering to Medical Devices”, a sample of 15 people to detect most of the problems in a user interface constitutes a practical minimum number of participants for human factors validation testing. This sample size theoretically provides the best possibility of detecting user interface design flaws while limiting the amount of resources required.

7. Arms and Interventions

Arm	Intervention/treatment
Experimental: Use of SaliPen medical device	Use according to self-decision.

8. Features to be studied

The points of interaction between the user and the device (User Interface) will be evaluated, including:

- the elements of the device with which the user interacts (i.e., those parts of the device that users see and touch), and
- the IFU (including packaging, labeling, User Manual, etc.).

The following parameters will be studied:

- Hazard: Potential source of harm, if any.
- Use error: User action or lack of action that was different from that expected by the manufacturer.

9. Outcome Measures

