Serious AEs include any events resulting in death, decreased life expectancy, life-threatening situations, persistent or permanent disability/incapacity, hospitalization, or congenital anomaly/birth defect or other important medical event. Within 24 hours, the Investigator will submit a written report documenting the circumstances of the serious AE.

While AE's and SAE's are not anticipated, should an incident occur during the visit or a subject report an event following the visit, the AE will be recorded in the subject's study records and followed to resolution.

12. Contacts and Locations

The subjects will randomly be recruited at clinical settings that deal with oral health, like dental or head and neck clinics. The outcome measure will be performed in this setting. Data will be collected on-site by the clinical staff.

13. Task Analysis

The Task Analysis breaks down the device use process into discrete sequences of tasks. The tasks will be analyzed to identify the user interface components involved, the use errors that users could make and the potential results of all use errors. The following task analysis is planned:

Phase	#	Task
I	1	Potential user knows the intended use of the study product.
	2	Potential user assesses correctly whether the study product is indicated for him/her.
	3	Potential user assesses correctly whether he/she can use the study product or not or conditioned to a medical advice.
II	1	User knows the maximum amount of times and the maximum length of time he/she can use the study product.
	2	User knows how to switch the study product ON and OFF.
	3	User knows how to place the study product into his/her mouth.
	4	User knows how to remove the study product from his/her mouth.
	5	Patient knows how to separate the intraoral and the extraoral units.
	6	Patients reports any significant discomfort felt with SaliPen
	7	Patients reports any significant difficultis in using SaliPen

Each task will be evaluated by the binary grading scheme satisfactory/unsatisfactory. The evaluator will be a member of the study team.

For Phase I - 100% success is needed to pass the evaluation for every subject.

For Phase II - 85% success rate is needed to pass the evaluation for every subject.

The Human Factor Study will be considered successful if 85% of the participants passed each Phase of the test.

14. Ethical and Legal Aspects

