	Neurologic disorder in the head and neck area (e.g., trigeminal neuralgia)		

Step 2: Self-Administered Questionnaire - Subject pre-purchase selection of the study product

Subjects will be asked to read the cover and the back cover of the device package and answer the following questions:

Question / Statement	Participant's answer	Correct answer	Success (1) / Failure (0)
1. Is the device for Dry Mouth Relief?	 Yes  No	 Yes  No	
2. Does the device fit your needs?	 Yes  No	 Yes  No	
3. If the device fits your needs, please check a box (only one):			
I can use the device	 Yes  No	 Yes  No	

Question / Statement	Participant's answer	Correct answer	Success (1) / Failure (0)
I cannot use the device because, either: 
 • I'm under 18 years of age. • I suffer from epileptic disorder. • I'm allergic to gold or silicone rubber. 	 Yes  No	 Yes  No	
I need professional advice before using the device because, either: 
 • I use a pacemaker. • I'm pregnant. • I suffer from a psychiatric or psychological disorder. • I suffer from an involuntary movement disorder (for example Parkinson's disease). • I have a neurologic disorder in the head and neck area (for example trigeminal neuralgia). 	 Yes  No	 Yes  No	

Step 3: Summary evaluation (to be completed by the evaluator)

Total questions/statements for those with dry mouth: 5

Number of correct answers: _____

Total questions/statements for those without dry mouth: 2

Number of correct answers: _____

Passed? (all answers/statements should be correct):

Yes
 No

Phase II

Subject I.D.: _____

Step 1: Oral soft tissue examination

EVALUATOR NAME: _____

DATE: _____

	Normal	Abnormal	If Abnormal, please specify findings
Labial Mucosa (including lips)			_____
Buccal Mucosa			_____
Mucogingival Folds			_____

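### Phase I's success rule and planned percentages do not separate unsafe from over-cautious self-selection, so with one or two at-risk subjects scored, Phase I can succeed although all of them choose unsafely

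*Combined protocol and SAP*

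**What the plan says.** The Statistical Analysis row of the synopsis (section 2) plans descriptive statistics only, to "calculate the percentage of correct answers and the percentage of subjects that passed the evaluation in each phase of the study". Section 13 sets the rules behind those figures:

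- Grading: "Each task will be evaluated by the binary grading scheme satisfactory/unsatisfactory".
- Subject level: "For Phase I - 100% success is needed to pass the evaluation for every subject".
- Phase level: "The Human Factor Study will be considered successful if 85% of the participants passed each Phase of the test".

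Section 6 gives the sample: "Phase I: 16 participants, 8 with xerostomia and 8 without xerostomia". The Phase I sheet in section 16 scores the two groups on different numbers of items: "Total questions/statements for those with dry mouth: 5" and "Total questions/statements for those without dry mouth: 2". The five appear to be question 1 (what the device is for), question 2 (whether it fits the subject's needs) and the three statements of question 3 (can use, cannot use, needs professional advice). The two are questions 1 and 2.

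Step 1 of the same sheet records each subject's contraindications and precautions. Step 2 puts the participant's answer beside the correct answer.

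**The concern.** Section 9 presents the Phase I outcome as validation that consumers can judge whether the product suits them, and task 3 of Phase I in section 13 is exactly the can-use, cannot-use or needs-advice judgement. For a switch to over-the-counter sale, the two directions of error on that task mean opposite things. A subject with a listed condition who ticks the can-use box has missed a warning. A subject with none who asks for advice has been too careful. Each is one failed subject.

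Phase I is the only test of the warnings. Its eligibility criteria admit adults with listed conditions, whereas Phase II excludes every one of those conditions (sections 2 and 10.2). An unsafe selection that the Phase I summary hides cannot come to light in Phase II.

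**Working it through.** Here, at risk means a dry-mouth subject with a contraindication or precaution recorded in Step 1.

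**Cut-off.** The documents give no whole-number cut-off for Phase I, but the Phase II sheet shows how 85% is rounded: 0.85 × 7 = 5.95, and the sheet requires 6 points (6/7 = 85.7%). The same rounding for 16 subjects gives 0.85 × 16 = 13.6, so 14 passes. 14/16 = 87.5% succeeds and 13/16 = 81.25% fails. Two failures of any kind are allowed.

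**Items lost per error.** An at-risk subject who ticks the can-use box is wrong on that statement and on the one that should have been ticked: 2 of 5 items. A subject with no listed condition who ticks needs-advice is wrong on that statement and on can-use: also 2 of 5.

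**Both planned percentages.** Scored items total 8 × 5 + 8 × 2 = 56. With k question 3 errors in one direction and everything else correct:

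| k | Subjects passed | Items correct | Phase I |
|---|---|---|---|
| 1 | 15/16 = 93.8% | 54/56 = 96.4% | succeeds |
| 2 | 14/16 = 87.5% | 52/56 = 92.9% | succeeds |
| 3 | 13/16 = 81.25% | 50/56 = 89.3% | fails |

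The rows are the same whether the k errors are all unsafe or all over-cautious. If all k at-risk subjects err unsafely, correct selection among those at risk is 0/k. With k = 1, one other subject may also fail and the phase still succeeds (14/16); with k = 2, none may.

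**How often 1 or 2 at-risk subjects would be scored.** Only the 8 dry-mouth subjects are scored on question 3. Enrolment is sequential with no quota for listed conditions, and no prevalence is given, so p is an assumption. P(1 or 2) = 8p(1−p)^7 + 28p²(1−p)^6, and P(0) = (1−p)^8:

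| Assumed p | P(none at risk) | P(1 or 2 at risk) |
|---|---|---|
| 5% | 66% | 33% |
| 10% | 43% | 53% |
| 20% | 17% | 63% |
| 30% | 6% | 49% |
| 40% | 2% | 30% |
| 50% | 0.4% | 14% |

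These are chances of an enrolment pattern. To see the difference, assume p = 20%, a 50% chance that each at-risk subject chooses unsafely, and 95% passing among the others.

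- k = 1: 0.3355 × 0.5 × P(at least 14 of 15 pass) = 0.3355 × 0.5 × 0.829 = 0.139
- k = 2: 0.2936 × 0.25 × 0.95^14 = 0.2936 × 0.25 × 0.488 = 0.036

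The full scenario then has a probability of about 17%, not 63%.

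**What a clean result could show.** With no unsafe selection among k at-risk subjects, the one-sided 95% upper limit for the unsafe rate is 1 − 0.05^(1/k): 95% for k = 1, 78% for k = 2, 63% for k = 3, 53% for k = 4 and 31% for k = 8.

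**The case against.** A reader might infer that the plan throws away the direction of error. It does not. The sheet keeps both answers, section 8 lists hazards and use errors among the parameters to be studied, and section 13 opens by saying that tasks will be analysed for possible use errors and their results. That is a real plan to look at error type and consequence, and this part of the objection stands. But neither section defines an unsafe selection, asks for a count over those at risk, or links the exercise to the success decision.

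It is also fair that errors of need are recorded apart from errors about restrictions. Section 13 lists them as separate tasks, the sheet scores question 2 on its own line, and the synopsis does not say whether percent correct is pooled or given per item. Per-item reporting would separate question 2 from question 3. It would not recover direction within question 3: a subject with a precaution who ticks can-use, and an unrestricted subject who ticks needs-advice, are wrong on the same two statements.

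The all-correct rule is strict, and an unsafe tick always fails that subject. The 85% rule then forgives up to two such subjects.

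Finally, separate reporting does not cure small numbers. With no quota for restricted users, the at-risk denominator may be 0, 1 or 2, and the upper limits above show how little that supports. This stands, and it limits what the fix can deliver.

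**Conclusion.** The point holds as a conditional statement. Under the plan's own rules, Phase I can be declared successful with 0% correct selection among at-risk subjects, and neither planned percentage would distinguish this from the same number of over-cautious errors. The conditions are that only 1 or 2 of the 8 dry-mouth subjects have a listed condition, all of them choose unsafely, and the other subjects stay within the remaining failure allowance.

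Two stronger readings are not supported. The first is that Phase I would succeed however many at-risk subjects choose wrongly; three such errors already give 81.25% and failure. The second is that the 14% to 63% range measures the risk of a misleading success. It is the chance of scoring exactly 1 or 2 at-risk subjects, it rests wholly on an assumed prevalence of 5% to 50%, and it says nothing about how often they would choose unsafely.

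The matter should be corrected before the study starts, because it determines what a Phase I success can be taken to show about restricted users.

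**What to change.** In the Statistical Analysis row and section 13, add a Phase I cross-table of the correct category derived from Step 1 (can use, cannot use, needs advice, no need) against the category chosen. Beside the pass rate, report:

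- unsafe selections, over the number of dry-mouth subjects with a listed condition;
- contraindicated subjects who chose needs-advice, which is neither a can-use tick nor over-caution;
- over-cautious errors;
- question 1 errors;
- question 2 errors, showing separately the restricted dry-mouth subjects who answered No, since some may have meant that they cannot use the device.

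State that the conclusion about restricted users rests on the at-risk count with its denominator, not on the pooled 85% rate, and that with few or no at-risk subjects it is inconclusive.

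The inputs are the Step 1 history and the Step 2 answers already on the sheet, so no new data or participants are needed. The cost is that a successful Phase I may have to be reported alongside unsafe selections, and the at-risk counts will be imprecise.

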3.1. The study objective

This is a Summative Evaluation aimed at evaluating the use of SaliPen (the study product) as an Over-The-Count (OTC) device rather than as a prescription device.

3.2. The study rationale

- Xerostomia (dry mouth) is the subjective feeling of oral dryness. The diagnosis by the practitioner is mostly relying on the patient's feeling.
- Most patients are elderly, many of them with limited mobility.
- Nowadays, those patients are at high risk for COVID-19 infection, morbidity and even mortality.
- The fear of exposure at the practitioner's clinic to obtain an Rx inhibits them from treating their xerostomia with the SaliPen.
- The cost of getting a prescription is an additional burden.
- The SaliPen is an OTC in other parts of the world for years.
- The performance of potential American users of an OTC SaliPen device will be evaluated in this usability study.

As a result, many patients leave their oral dryness untreated, with the well-known consequences of poor oral functions, oral health, daily suffering, and more.

4. Brief Study Description

This Human Factors Validation Testing will assess user interactions to verify the capability of potential users to assess if the study product fits their needs and if they can use it correctly based on the provided Information For User (IFU)?

More specifically, this is a non-comparative case series study and is subdivided into two major parts. Those parts are:

- 1- Phase I: aimed at testing if, based on the IFU, the potential subjects can decide whether the study product is or is not appropriate to treat their condition and,
- 2- Phase II: aimed at assessing whether the users can use the study product correctly without counseling by a health care provider.

Condition or disease	Intervention/treatment
Xerostomia	SaliPen

5. Detailed Study Description

5.1. Phase I

To simulate an OTC setting, potential subjects will be requested to read the label text on the outside of the study product package (external labeling) and determine whether the study product addresses their needs, without a provider direction or assistance.

5.2. Phase II

The study product will be dispensed only to those subjects who will indicate that they volunteerize to participate in this phase of the study.

At Phase II subjects with xerostomia and that are willing to try the study product, will be requested to use it with no training, except for their understanding of the User Manual (internal labeling). Those subjects will use the study product in a supervised clinical setting. Subjects who report any discomfort will be offered the option to pause and remove the device upon such a request.

Correct use verification will be performed by the study investigators. Subjects will answer questions regarding product use, clarity of the IFU, ease of use, etc. Subjects will also receive an exam of their oral cavity.

6. Study Design

Study Type:	Interventional (Clinical Trial)
Enrollment:	Phase I: 16 participants, 8 with xerostomia and 8 without xerostomia
	Phase II: 16 participants with xerostomia (may include participants in Phase I with xerostomia)
Allocation:	N/A
Intervention Model:	Single Group Assignment
Masking:	None (Open Label)
Primary Purpose:	Human Factor Validation - Usability Engineering assessment for OTC labeling
Official Title:	SaliPen Usability Engineering Study for OTC labeling
Study Start Date:	TBD

According to the FDA Guidance document “Applying Human Factors and Usability Engineering to Medical Devices”, a sample of 15 people to detect most of the problems in a user interface constitutes a practical minimum number of participants for human factors validation testing. This sample size theoretically provides the best possibility of detecting user interface design flaws while limiting the amount of resources required.

7. Arms and Interventions

Arm	Intervention/treatment
Experimental: Use of SaliPen medical device	Use according to self-decision.

8. Features to be studied

The points of interaction between the user and the device (User Interface) will be evaluated, including:

- the elements of the device with which the user interacts (i.e., those parts of the device that users see and touch), and
- the IFU (including packaging, labeling, User Manual, etc.).

The following parameters will be studied:

- Hazard: Potential source of harm, if any.
- Use error: User action or lack of action that was different from that expected by the manufacturer.

9. Outcome Measures

1. Percentage of participants who appropriately will self-select the study product for use under simulated OTC conditions [Phase I]. Following the standard norms for the Rx-to-OTC switch process, this outcome is a validation of potential consumers' ability to self-diagnose the condition and to decide that treatment with the product is appropriate for them.
2. Percentage of participants who correctly will use the study product when dispensed under simulated OTC conditions [Phase II]. Correct use means that the participants will demonstrate the use of the study product according to the guidelines outlined in the User Manual. Following the standard norms for the therapy of Rx-to-OTC switch process, this outcome is a validation of potential consumers' ability to self-treat with the product according to the product's supplied IFU.

10. Eligibility Criteria

Ages Eligible for Study: 18 years of age and older for Phase I and Phase II

Genders Eligible for Study: Female and male

10.1. Inclusion criteria:

- 1- For Phase I: 8 subjects with xerostomia and 8 without that are 18 years old or older
- 2- For Phase II: Subjects with xerostomia that are 18 years old or older

10.2. Exclusion criteria:

- 1- For Phase I:
 - Children and adolescents (persons under 18 years of age)
 - Persons with experience in the use of SaliPen

2- For Phase II: Subjects for whom the study product is not indicated and/or do not agree to participate in Phase II. For the avoidance of doubt, the following conditions are exclusion criteria:

- Persons with experience in the use of SaliPen
- Children and adolescents (persons under 18 years of age)
- Epileptic disorder
- Persons that are allergic to the surface materials of the device
 - Electrodes: coated with gold
 - Body: made of methyl vinyl silicone rubber
- Use of a pacemaker
- Pregnancy
- Psychiatric or psychological disorders
- Involuntary muscle movement disorder (such as Parkinson's)
- Neurologic disorder in head and neck area

11. Reportable Events

An adverse event (AE) is defined as any untoward medical occurrence in a subject during the investigation. Any findings will be documented on the AE CRF.

Serious AEs include any events resulting in death, decreased life expectancy, life-threatening situations, persistent or permanent disability/incapacity, hospitalization, or congenital anomaly/birth defect or other important medical event. Within 24 hours, the Investigator will submit a written report documenting the circumstances of the serious AE.

While AE's and SAE's are not anticipated, should an incident occur during the visit or a subject report an event following the visit, the AE will be recorded in the subject's study records and followed to resolution.

12. Contacts and Locations

The subjects will randomly be recruited at clinical settings that deal with oral health, like dental or head and neck clinics. The outcome measure will be performed in this setting. Data will be collected on-site by the clinical staff.

13. Task Analysis

The Task Analysis breaks down the device use process into discrete sequences of tasks. The tasks will be analyzed to identify the user interface components involved, the use errors that users could make and the potential results of all use errors. The following task analysis is planned:

Phase	#	Task
I	1	Potential user knows the intended use of the study product.
	2	Potential user assesses correctly whether the study product is indicated for him/her.
	3	Potential user assesses correctly whether he/she can use the study product or not or conditioned to a medical advice.
II	1	User knows the maximum amount of times and the maximum length of time he/she can use the study product.
	2	User knows how to switch the study product ON and OFF.
	3	User knows how to place the study product into his/her mouth.
	4	User knows how to remove the study product from his/her mouth.
	5	Patient knows how to separate the intraoral and the extraoral units.
	6	Patients reports any significant discomfort felt with SaliPen
	7	Patients reports any significant difficultis in using SaliPen

Each task will be evaluated by the binary grading scheme satisfactory/unsatisfactory. The evaluator will be a member of the study team.

For Phase I - 100% success is needed to pass the evaluation for every subject.

For Phase II - 85% success rate is needed to pass the evaluation for every subject.

The Human Factor Study will be considered successful if 85% of the participants passed each Phase of the test.

14. Ethical and Legal Aspects

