Gingival Mucosa			_____
Edentulous Ridge/Retromolar area			_____
Tongue			_____
Sublingual Area/floor of mouth			_____
Submandibular area			_____

Step 2: Assessment of subject performance
EVALUATOR NAME: _____

DATE: _____

Please evaluate how the participant addresses the following questions/tasks:

Questions	Participant's answer	Correct answer	Success (1) / Failure (0)
1. How many times in a day and how many minutes (maximum time) you can use the device in one session?			
Tasks	Evaluation		Success (1) / Failure (0)
2. How do you turn on ON and OFF the device?			
3. How do you insert the device in your mouth?			
4. How do you take the device out of your mouth?			
5. How do you detach and reattach the white extraoral command unit from the blue intraoral stimulating unit?			
Subject assessment (place an x where relevant for you) Note: Success (1) is meant if options 2 or 3 were chosen Failure (0) is meant if option 1 was chosen			Success (1) / Failure (0)
6. Did you experience discomfort with the SaliPen in your mouth?	1- Severe discomfort 2- Moderate discomfort 3- No discomfort		
7. Did you experience difficulties in using the SaliPen?	1- Severe discomfort 2- Moderate discomfort 3- No discomfort		

Summary evaluation:
Total questions/tasks/self-assessments: 7

Number of points: _____

Passed? (minimum 6 points):

Yes
 No

Step 3: Oral soft tissue examination

EVALUATOR NAME: _____

DATE: _____

	Normal	Abnormal	If Abnormal, please specify findings
Labial Mucosa (including lips)			
Buccal Mucosa			
Mucogingival Folds			
Gingival Mucosa			
Edentulous Ridge/Retromolar area			
Tongue			
Sublingual Area/floor of mouth			
Submandibular area		

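### Phase II can succeed while every participant fails the same task, and no per-task result, instructions-clarity question or error-cause field is tied to that success

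*Combined protocol and SAP*

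**What the plan says.** Section 8 names two parameters to be studied: "Hazard: Potential source of harm, if any" and "Use error: User action or lack of action that was different from that expected by the manufacturer". Section 13 says the tasks will be analysed "to identify the user interface components involved, the use errors that users could make and the potential results of all use errors". Section 5.2 adds: "Subjects will answer questions regarding product use, clarity of the IFU, ease of use, etc".

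On scoring, Section 13 states: "Each task will be evaluated by the binary grading scheme satisfactory/unsatisfactory". The two Phases then differ. "For Phase I - 100% success is needed to pass the evaluation for every subject", whereas a Phase II participant needs 85%. The Phase II evaluation sheet in Section 16 turns that into "Passed? (minimum 6 points", out of 7. The study succeeds if 85% of participants pass each Phase.

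The Statistical Analysis row of the synopsis (Section 2) plans two descriptive outputs for each Phase: the percentage of answers that are correct and the percentage of participants who pass. Section 9 defines correct use, the Phase II outcome, as demonstrated use in line with the User Manual.

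**The concern.** A usability validation is meant to find the step that many users get wrong for the same reason. A participant-level pass mark that forgives one miss in seven does not distinguish scattered slips from one shared error. A step that the manual explains badly could be failed by everyone, and Phase II would still meet its criterion.

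The conclusion at stake is that people can use the device from the manual alone, without counselling. It would be stated for a set of tasks that includes one nobody performed correctly. If the reason for the error is not asked at the visit, it may not be recoverable afterwards.

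**Working it through.** **Inputs.** Seven Phase II items (Section 16): one knowledge question (item 1), four tasks (items 2–5) and two self-ratings (items 6–7, failed only at the severe option). Sixteen participants (Section 6). The 85% rules are in Section 13.

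**The plan's own pass mark.** 6/7 = 85.7% meets 85% and 5/7 = 71.4% does not, so the minimum of 6 points is reproduced. At Phase level, 14/16 = 87.5% meets 85% and 13/16 = 81.3% does not, so 14 passes are needed.

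**Shared error in Phase II.** Suppose all 16 fail one of items 1–5 and succeed on the other six.
- Each participant scores 6/7 and passes: 16/16 = 100%.
- Result on that task: 0/16.
- Pooled percentage correct: (16 × 6)/(16 × 7) = 96/112 = 85.7%.

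**How much depends on the other items.** With one task failed by everyone, a participant passes only if the other six are all correct. If each succeeds independently with probability q (an assumption; the plan gives no rates), the chance of passing is q^6, and Phase II succeeds with probability P(X ≥ 14), X ~ Binomial(16, q^6).

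| q | q^6 | P(Phase II succeeds) |
|---|---|---|
| 1.00 | 1.000 | 1.000 |
| 0.99 | 0.942 | 0.937 |
| 0.98 | 0.886 | 0.727 |
| 0.95 | 0.735 | about 0.16 |

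**Where the slack comes from.** On the five objective items alone, one miss gives 4/5 = 80%, below 85%. The two self-ratings lift one miss to 6/7.

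**Phase I.** Every answer must be correct, so any error fails the participant. At most 16 − 14 = 2 participants can make any error if the Phase is to succeed.

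**Promises against forms.**
- Clarity of the instructions: promised in Section 5.2; no item in Section 15 or 16.
- Ease of use: item 7 asks about difficulties but offers discomfort options.
- What the error was: the sheets set the participant's answer beside the correct one for Phase I and for Phase II item 1, and give a free evaluation column for tasks 2–5.
- Why it happened and what harm could follow: no field.

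**A per-task flag at more than 2 failures of 16.** This applies the plan's 85% to each task, which the plan itself does not do. If a task has true error rate e, the chance of a flag is 1 − P(X ≥ 14), X ~ Binomial(16, 1 − e): 1 − 0.957 = 0.043 at e = 5%, 1 − 0.789 = 0.211 at 10%, 1 − 0.352 = 0.648 at 20%, 1 − 0.099 = 0.901 at 30%, and 1 − 0.002 = 0.998 at 50%. With the other items perfect, the current rule gives Phase II success with probability 1 at every one of these rates.

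**The case against.** Several stronger readings are tempting, and the documents do not support them.

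- A reader might infer that the error disappears from the results. The planned percentage of correct answers could be meant per item, and 0/16 would then be plain to see. What stands is that the text does not say which is meant and that no threshold or consequence attaches to a single task.
- A reader might infer that the forms record nothing about an error. They do record the wrong answer in Phase I and for Phase II item 1, and they leave room for a description on tasks 2–5. Only cause and possible harm lack a field.
- A reader might infer that hazards and clarity are collapsed into 0/1 points. Neither is scored at all. Harm that actually occurs is captured on the adverse event form (Section 11, not reproduced) and by oral examination before and after use. Neither route is described as recording potential harm from a use error.
- A reader might take Section 13 as a promise to analyse observed errors. Its wording concerns errors that users could make, which fits a prospective task analysis equally well. Section 8 is the firmer basis.
- A reader might extend the problem to Phase I. The 100% rule excludes it.

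The strongest remaining objection is that the extreme case is unlikely: at 95% success on the other items, Phase II would probably fail anyway. That limits how often the rule misleads. It does not change the fact that failures on one task, however many, cannot by themselves stop Phase II from succeeding.

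**Conclusion.** The point holds for Phase II. As written, 16/16 participants can pass with 0/16 on one User Manual task, and a pooled percentage correct of 85.7% would not reveal it. That sits badly with the Section 9 definition of correct use and with the Section 6 reason for the sample size. The 16/16 figure assumes no other failures. Under independence, success remains likely if the other items are passed 98–99% of the time (0.727 to 0.937) and unlikely at 95% (about 0.16).

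Two gaps need no such assumption. The clarity question promised in Section 5.2 is missing from every questionnaire and evaluation sheet in the document. Use error and hazard are listed as parameters, yet those forms have no field for the reason for an error or its potential harm.

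**What to change.** 1. In the Statistical Analysis text, specify the percentage correct per task for each Phase, as k/16. In Phase I, the three statements under question 3 count only for participants with dry mouth, so their denominator is 8. In Phase II, show items 1–5 separately from self-ratings 6–7.
2. In Section 13, state that Phase II success is reported only together with this table. State also that any task failed by more than 2 of 16 (13/16 = 81.3%, below the plan's own 85%) is reported as an unresolved user-interface problem, so that correct use is not claimed for that task. The pass marks can stay as they are.
3. Add one question on clarity of the instructions, asked after Phase II scoring so that it cannot influence the score.
4. Add one field for the reason for, and possible consequence of, each failed task. List all observed use errors from the existing answer and evaluation columns.

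The cost is one question, one field, one table and one listing, with no change in sample size. The real downside for the sponsor is a possibly less favourable conclusion: a task with a true error rate of 10% would be flagged about 21% of the time.
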